6.5. Analysis of medically attended RTIs

The analysis will be performed on the ES by study group.

The proportion of subjects with at least one medically attended RSV-associated RTI (with 95 % CI) will be calculated.

Viral load assessed by the quantitative PCR (RSV-A/B) of RSV-RTI cases will be listed for any cases where this assay is performed.

Medically attended RSV-associated RTI co-infected or colonisation with another viral etiology identified by multiplex PCR will be described.

Medically attended RTI with any viral etiology identified by multiplex PCR will be described.

The proportion of subjects (with 95% CI) with at least one medically attended RTI (all causes) will be calculated by group.

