3.2. Secondary objectives

- To evaluate the reactogenicity and safety of a single intramuscular dose of the RSV investigational vaccines up to study conclusion.
- To evaluate the immunogenicity of a single intramuscular dose of the RSV investigational vaccines up to 90 days after vaccination (Day 90).
- To further assess the safety of the investigational RSV vaccines by evaluating whether a single dose of the vaccines induces antibodies against the residual host cell protein neogenin (NEO) up to 1 month post-vaccination (Day 30).
- To estimate the incidence of medically attended RSV-associated RTIs up to study conclusion.

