4.2. Secondary

- Occurrence of AEs from vaccination up to study conclusion:
 - Occurrence of each solicited local and general AE, during a 7-day follow-up period after vaccination (i.e. the day of vaccination and 6 subsequent days), for all subjects in all groups;
 - Occurrence of any unsolicited AE, during a 30-day follow-up period after vaccination (i.e. the day of vaccination and 29 subsequent days), for all subjects in all groups;
 - Occurrence of any haematological (haemoglobin level, White Blood Cells [WBC], lymphocyte, neutrophil, eosinophil and platelet count) and biochemical (alanine amino-transferase [ALT], aspartate amino-transferase [AST] and creatinine) laboratory abnormality at Day 0, Day 7, Day 30, Day 60 and Day 90 for all subjects in all groups;
 - Occurrence of any SAE, for all subjects in all groups.
- Functional antibody titres against RSV for all subjects in all groups:
 - Neutralising antibody titres against RSV-A at Day 0, Day 30, Day 60 and Day 90;
 - Neutralising antibody titres against RSV-B at Day 0, Day 30, Day 60 and Day 90.
- PCA concentration at Day 0, Day 30, Day 60 and Day 90 for all subjects in all groups.
- Humoral immune response to the residual host cell protein NEO in the investigational RSV vaccine at pre-vaccination (Day 0), and 1 month post-vaccination (Day 30) for all subjects in all groups.
 - Antibody concentrations against NEO
- Occurrence of medically attended RSV-associated RTIs up to study conclusion

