6.5. Analysis of medically attended RTIs

The analysis will be performed on the ES by study group.

The proportion of subjects (with 95% CI) with at least one medically attended RTI (all causes) will be calculated by group.

Viral load assessed by the quantitative PCR (RSV-A/B) of RSV-RTI cases will be listed for any cases where this assay is performed.

Medically attended RSV-associated RTI co-infected or colonisation with another viral etiology identified by multiplex PCR will be described.

Medically attended RTI with any viral etiology identified by multiplex PCR will be described.

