9. CHANGES FROM PLANNED ANALYSES

In order to align to ICH and CDISC terminology the Total Vaccinated Cohort and the According To Protocol cohort have been renamed Exposed Set (ES) and Per-Protocol Set (PPS) respectively.

Changes in Amendment 1 mainly include the following.

For the sequence of analysis, the IDMC evaluation was newly added to review all available safety and reactogenicity data (including Day 30 haematology and biochemistry parameters) of all enrolled subjects up to at least 30 days post administration of the study vaccine or placebo.

Since the document of criteria for eliminating subjects from analysis will not be used anymore, the table of Elimination codes has been modified for more clarity. Attribution of code 1070 to a subject requires CRDL confirmation. Attribution of these elimcodes including 1040, 2040, 2050, 2060, 2070 and 2120 to subject need CRDL review of individual data listings.

In the analysis of immunogenicity section, the distribution of fold increase of the antibody titres against RSV-A and RSV-B and concentrations against NEO have been added.

For the analysis of safety, the percentage of subjects reporting each individual solicited local AE (any, each grade, resulting in medically attended visit) during the 7-day follow-up period after vaccination will also be tabulated based on maximum intensity per subject for each study vaccine group; the percentage of subjects reporting each individual solicited general AE (any, each grade, any related, any Grade 2 related, any Grade 3 related, resulting in medically attended visit) during the 7-day follow-up period after vaccination will also be based on maximum intensity per subject for each study vaccine group.

Evaluation of last secondary objective 'To estimate the incidence of medically attended RSV-associated RTIs up to study conclusion' will be performed based on MA-RTIs rather than MA-RSV associated RTIs.

The cut-off for the updated (qualified) version of the PCA assay will be set at the level of the assay LLOQ (9.60 µg/mL). Hence the SAP does not need to define handling of data between the LOD and LLOQ anymore, as results will only be provided as of the LLOQ. It only needs to be defined that for results below the cut-off (LLOQ), an arbitrary value of half of the cut-off will be considered for calculation of GMC and fold increase.

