- *In the analysis of safety section, analysis on ‘Number and percentage of subjects reporting the occurrence of medically attended respiration tract infections (MARTIs), during the 30-day, 60-day or 90-day post-vaccination period and up to study end’ will be reported; Therefore, ‘Number and percentage of subjects reporting one medically attended RSV-associated RTI and medically attended RTI (all causes) within the 30-day post-vaccination period or throughout the study period’ will not be generated;*
- *In the analysis of medically attended RTIs, viral load assessed by the quantitative PCR (RSV-A/B) of RSV-RTI cases will be only listed in the individual listings; therefore, analysis on ‘Descriptive statistics of the viral load assessed by the quantitative PCR (RSV-A/B) of RSV-RTI cases (All vaccinated subjects)’ will not be reported;*
- *In the analysis of immunogenicity section, tables/figures related to the analysis of RSV-B will be added;*
- *In the analysis of immunogenicity section, tables/figures related to the analysis of the IgG total and IgG1 subclass will be added;*
- *In the analysis of immunogenicity section, tables related to the analysis of anti-RSV A and anti-PCA in the subset of subjects with IgG/IgG1 data available will be added.*

Changes in Amendment 2 mainly include the following.

- *In the analysis of immunogenicity section, the analysis on GM ratios between anti-RSV F antibody concentrations (IgG Total) and anti-RSV-A neutralising antibody titers at pre-vaccination has been added for Day 90 and final analysis;*
- *In the analysis of immunogenicity section, the analysis on GM ratios of fold increase post/pre (Day 30/Day 0) between anti-RSV F antibody concentrations (IgG Total) and anti-RSV-A neutralising antibody titers has been added for Day 90 and final analysis.*

Changes of TFL/TOC

- *In the analysis of safety section, figures of “Individual results of hemoglobin levels beyond grade 2” will be reported for Day 90 and final analysis to replace the figures of “Individual results of hemoglobin levels outside of normal range”;*
- *In the analysis of safety section, figures of “Individual results of white blood cells counts levels lower than LL” and figures of “Individual results of white blood cells counts levels higher than UL” will be reported for Day 90 and final analysis to replace the figures of “Individual results of white blood cells counts levels outside of normal range”.*

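### The SAP keeps RSV-associated medically attended RTI as a secondary objective and endpoint but plans a proportion with confidence interval only for all-cause RTI

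*SAP*

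**What the plan says.** All references are to SAP Amendment 4 unless stated otherwise.

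- Section 3.2, last secondary objective: "To estimate the incidence of medically attended RSV-associated RTIs up to study conclusion".
- Section 4.2, last secondary endpoint: "Occurrence of medically attended RSV-associated RTIs up to study conclusion".
- Section 6.5, the only proportion with an interval: "The proportion of subjects (with 95% CI) with at least one medically attended RTI (all causes) will be calculated by group". What remains for RSV is a listing, "Viral load assessed by the quantitative PCR (RSV-A/B) of RSV-RTI cases will be listed for any cases where this assay is performed", and descriptions of RSV-associated RTIs with another virus present and of RTIs by viral aetiology on multiplex PCR.
- Section 9, under the Amendment 1 changes: evaluation of that objective "will be performed based on MA-RTIs rather than MA-RSV associated RTIs". The same section says that a table titled "Number and percentage of subjects reporting one medically attended RSV-associated RTI and medically attended RTI (all causes) within the 30-day" (the title continues to cover the whole study period) will not be produced, because MA-RTI tables for 30, 60 and 90 days and up to study end take its place.
- Section 2: nasal swabs are taken for MA-RTIs from enrolment to study end.
- Section 11.1: intervals for a within-group proportion are Clopper-Pearson exact, two-sided 95%.

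**The concern.** The objective and endpoint name one quantity and the analysis section estimates another. A programmer who follows section 6.5 will deliver an all-cause proportion under an RSV-associated objective. The study report would then either present that figure as the answer to 3.2 or leave the RSV figure to be assembled afterwards from listings and descriptions, without a fixed case definition, denominator or interval. In a trial of an RSV vaccine, the RSV-specific count by arm is the more informative of the two, and the swabs and PCR needed to produce it are already part of the plan.

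**Working it through.** **1. Are the two quantities the same?** They are not. Every subject with an RSV-associated MA-RTI is also a subject with an MA-RTI of any cause. With the same group denominator n from the Exposed Set,

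p(RSV) = x(RSV)/n ≤ x(all)/n = p(all).

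The all-cause proportion therefore bounds the RSV proportion from above. It equals it only if every subject counted had at least one RSV-positive episode. The SAP gives no RTI rate and no split by virus, so the width of that gap is unknown.

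**2. Is the RSV proportion planned elsewhere in the current version?**

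| Place (Amendment 4) | Quantity | Proportion with CI by group? |
|---|---|---|
| 3.2, 4.2 | RSV-associated MA-RTI | Named as objective and endpoint |
| 6.5, proportion | All-cause MA-RTI | Yes |
| 6.5, viral load | RSV cases where the assay was run | No, listing |
| 6.5, multiplex PCR | RSV co-infection; any viral aetiology | No, described |
| 9, replacement tables | MA-RTI | Not RSV-specific |
| 9, withdrawn table | RSV-associated and all-cause | Not produced |
| Annex 4 template list | No RSV-associated RTI template | No |

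The separate TFL table of contents is not reproduced in the SAP. The finding rests on what sections 6.5 and 9 and Annex 4 state.

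**3. Is a reason given?** Section 9 records the change of case definition without explanation. Its only stated ground for dropping the RSV table is that the MA-RTI tables will be reported. Section 8 promises that changes will be described and justified in the final study report, which does not supply a reason in the plan itself.

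**4. Could small numbers make the RSV proportion impossible to estimate?** The SAP does not say so. Its own method can be applied. For x cases in n subjects, the lower limit is the 2.5% quantile of Beta(x, n−x+1) and the upper limit the 97.5% quantile of Beta(x+1, n−x). For x = 0 the lower limit is 0 and the upper limit is 1 − 0.025^(1/n). Group size is about 100 (Table 1). The case counts below are assumptions.

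| Cases in 100 | Exact 95% CI |
|---|---|
| 0 | 0 to 3.62% |
| 1 | 0.03 to 5.45% |
| 2 | 0.24 to 7.04% |
| 5 | 1.64 to 11.28% |

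For zero cases: 1 − 0.025^(1/100) = 1 − 0.9638 = 3.62%. A group with no RSV case still yields a usable bound.

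**The case against.** The strongest reply is that the change is disclosed and RSV has not disappeared. Section 9 names the objective, says how it will be evaluated and identifies the withdrawn table. Section 6.5 works on the Exposed Set by group and still describes viral aetiology by multiplex PCR, which would include RSV. A reader could therefore count RSV cases per group against a known denominator. This stands as far as it goes. It would be wrong to infer that the switch is hidden or that the report will contain nothing on RSV cases. But disclosure did not bring 3.2 and 4.2 into line, and a count assembled by hand from descriptions is not a pre-specified estimate.

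A second reply is that Amendment 2 is no evidence of a late loss. Its section 6.5 still said "The proportion of subjects with at least one medically attended RSV-associated RTI (with 95 % CI) will be calculated", but its section 9 already carried the substitution, so removing that line in Amendment 3 brought 6.5 into agreement with a recorded decision. That is fair, and the text is superseded. The point rests only on Amendment 4.

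Third, RSV status depends on the subject contacting the investigator and on a swab within 72 hours of the medical attendance (section 2), so some episodes may have no result. This is also fair. It calls for showing how many MA-RTIs were tested; it does not justify dropping the estimate.

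Finally, the current SAP cites Protocol Amendment 1, which is not at hand. A reason for the change may be given there.

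**Conclusion.** The mismatch is real in the current text. Sections 3.2 and 4.2 promise an RSV-associated incidence, and sections 6.5 and 9 plan an interval only for all-cause MA-RTI, without a scientific reason. The missing piece is specific: an RSV-associated proportion with a 95% CI by group.

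Two stronger readings are tempting and should not be drawn. One is that the reported figure would be several times the RSV rate because most RTIs are due to other viruses. The SAP gives no rates and no aetiology split, so no ratio can be stated. The other is that a vaccine-placebo contrast in RSV disease would be diluted. No such contrast is planned: the objective is to estimate incidence, section 6.5 gives by-group proportions, and section 7 makes all comparisons descriptive.

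This should be fixed, but it does not threaten the primary analysis. The endpoint is not part of the desirability index in section 6.4 and no decision rule depends on it. The 3.6% limit assumes zero cases and 100 subjects in a group. It shows only that the estimate is feasible.

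**What to change.** In section 6.5 and the final tables, restore by study group the number and percentage of subjects with at least one PCR-confirmed RSV-associated MA-RTI from Day 0 to study conclusion, with Clopper-Pearson 95% CI. Next to it, give the number of MA-RTIs and the number with a swab tested, so that missing RSV status is visible. Keep the all-cause proportion as supportive. Record the reversal as a new entry in section 9, leaving the existing entry as the record of the previous decision.

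If all-cause MA-RTI is what the sponsor intends, amend the objective in 3.2 and the endpoint in 4.2 to say so and state the reason.

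The first option costs one table from swab and PCR data already planned, plus a few lines of SAP text. The second costs wording only, but gives up the RSV-specific objective.

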7. ANALYSIS INTERPRETATION

All comparative analyses will be descriptive with the aim to characterise the difference in reactogenicity/immunogenicity between groups. These descriptive analyses should be interpreted with caution considering that there is no adjustment for multiplicity for these comparisons.

8. CONDUCT OF ANALYSES

Any deviation(s) or change(s) from the original statistical plan outlined in this protocol will be described and justified in the final study report.

8.1. Sequence of analyses

The statistical analyses will be performed in several steps:

- In preparation of the planned iSRC evaluation, analysis of safety and reactogenicity data up to at least 7 days post-vaccination of the first 25% of all subjects will be performed (see Section 8.10.2 of the Protocol for more information).
- *In preparation of the planned IDMC evaluation, analysis of safety and reactogenicity data (including haematology/ biochemistry parameters) up to at least 30 days post-vaccination of all enrolled subjects will be performed.*

- The first main analysis on all subjects will be performed when all data up to 30 days post-vaccination are available (primary endpoints). In order to maintain the blind, this analysis by group will be performed by an independent statistician and the results which would lead to the unblinding of some subjects (e.g. a specific AE reported by one subject only) will be blinded (i.e. the group in which this event occurred will not be identified). No individual data listings will be provided.
- A second analysis will be performed when all data up to 90 days post-vaccination are available (secondary endpoints). At this point, the GSK statistician will be unblinded (i.e. will have access to the individual subject treatment assignments), but no individual listings will be provided. Given that summary results may unblind some specific subjects, the study will be conducted in a single-blind manner from this point onwards, with subjects remaining blinded up to study conclusion and the investigators will not have access to the treatment allocation up to study conclusion.
- The final analysis will be performed when all data up to study conclusion are available. All available tertiary endpoints will also be analysed in this step. Individual listings will only be provided at this stage.
- An integrated study report presenting all analyses will be written and made available to the investigators at the time of final analysis.
- If data for tertiary endpoints become available at a later stage, (an) additional analysis/analyses will be performed. These data will be documented in Annex(es) to the study report and will be made available to the investigators at that time.

Description	Analysis ID	Disclosure Purpose (CTRS=web posting, SR=study report, internal)	Dry run review needed (Y/N)	Study Headline Summary (SHS) requiring expedited communication to upper management (Yes/No)	Reference for TFL
Final Analysis	E1_01	Study report CTRS	N	Yes	All tables from TFL dated 01JUN2018
Analysis of Day 30	E1_04	Internal CTRS	N	Yes	All tables from TFL dated 13NOV2017
Analysis of Day 90	E1_05	Internal CTRS	N	Yes	All tables from TFL dated 13NOV2017

8.2. Statistical considerations for interim analyses

No interim analysis will be performed.

9. CHANGES FROM PLANNED ANALYSES

In order to align to ICH and CDISC terminology the Total Vaccinated Cohort and the According To Protocol cohort have been renamed Exposed Set (ES) and Per-Protocol Set (PPS) respectively.

Changes in Amendment 1 mainly include the following.

For the sequence of analysis, the IDMC evaluation was newly added to review all available safety and reactogenicity data (including Day 30 haematology and biochemistry parameters) of all enrolled subjects up to at least 30 days post administration of the study vaccine or placebo.

Since the document of criteria for eliminating subjects from analysis will not be used anymore, the table of Elimination codes has been modified for more clarity. Attribution of code 1070 to a subject requires CRDL confirmation. Attribution of these elimcodes including 1040, 2040, 2050, 2060, 2070 and 2120 to subject need CRDL review of individual data listings.

In the analysis of immunogenicity section, the distribution of fold increase of the antibody titres against RSV-A and RSV-B and concentrations against NEO have been added.

For the analysis of safety, the percentage of subjects reporting each individual solicited local AE (any, each grade, resulting in medically attended visit) during the 7-day follow-up period after vaccination will also be tabulated based on maximum intensity per subject for each study vaccine group; the percentage of subjects reporting each individual solicited general AE (any, each grade, any related, any Grade 2 related, any Grade 3 related, resulting in medically attended visit) during the 7-day follow-up period after vaccination will also be based on maximum intensity per subject for each study vaccine group.

Evaluation of last secondary objective 'To estimate the incidence of medically attended RSV-associated RTIs up to study conclusion' will be performed based on MA-RTIs rather than MA-RSV associated RTIs.

The cut-off for the updated (qualified) version of the PCA assay will be set at the level of the assay LLOQ (9.60 µg/mL). Hence the SAP does not need to define handling of data between the LOD and LLOQ anymore, as results will only be provided as of the LLOQ. It only needs to be defined that for results below the cut-off (LLOQ), an arbitrary value of half of the cut-off will be considered for calculation of GMC and fold increase.

Algorithm for handling of data of RSV-B neutralising antibody titres between the LOB and LLOQ is defined as similar as for RSV-A by considering the LOB for RSV-B is 6.

Additional analysis of the IgG total and IgG1 subclass and analysis of anti-RSV A and anti-PCA in the subset of subjects with IgG/IgG1 data have been added.

Changes of TFL/TOC

- *In the analysis of safety section, figures of ‘Individuals results of haematological (haemoglobin level, white blood cells and platelet count) and biochemical (ALT, AST and creatinine) parameters outside of the normal ranges in each group’ has been added to replace the figures of ‘Mean profile of haematological and biochemical parameters change from baseline (Day 0)’;*
- *In the analysis of safety section, the titles in all tables reporting ‘Incidence and nature of symptoms (solicited and unsolicited) during the 7-day and 30-day post-vaccination period’ have been changed from ‘with causal relationship to’ to ‘considered related to vaccination’;*
- *In the analysis of safety section, analysis on ‘Incidence of solicited local/general symptoms reported during the 7-day post-vaccination period’ will be summarized based on maximum intensity for each grade per subject for each group; therefore, analysis on ‘incidence of solicited local/general symptoms reported during the 7-day post-vaccination period, including \geq grade 2 category’ will not be generated.*
- *In the analysis of safety section, analysis on ‘Number (%) of subjects reporting the occurrence of adverse events within the 7-day and 30-day post-vaccination period’ will be added.*
- *In the analysis of safety section, analysis on ‘Number (%) of subjects with serious adverse events during the study period including number of events reported’ and ‘Number (%) of subjects with serious adverse events considered related to vaccination during the study period including number of events reported’ by %UNSOL (EVENT=1) will not be reported because %CTR_SAE macro has been adapted to generate SAE, related SAE, fatal SAE and related fatal SAE.*
- *In the analysis of safety section, analysis on ‘Number and percentage of subjects reporting the occurrence of medically attended respiration tract infections (MARTIs), during the 30-day, 60-day or 90-day post-vaccination period and up to study end’ will be reported; Therefore, ‘Number and percentage of subjects reporting one medically attended RSV-associated RTI and medically attended RTI (all causes) within the 30-day post-vaccination period or throughout the study period’ will not be generated;*
- *In the analysis of medically attended RTIs, viral load assessed by the quantitative PCR (RSV-A/B) of RSV-RTI cases will be only listed in the individual listings; therefore, analysis on ‘Descriptive statistics of the viral load assessed by the quantitative PCR (RSV-A/B) of RSV-RTI cases (All vaccinated subjects)’ will not be reported;*
- *In the analysis of immunogenicity section, tables/figures related to the analysis of RSV-B will be added;*
- *In the analysis of immunogenicity section, tables/figures related to the analysis of the IgG total and IgG1 subclass will be added;*
- *In the analysis of immunogenicity section, tables related to the analysis of anti-RSV A and anti-PCA in the subset of subjects with IgG/IgG1 data available will be added.*

Changes in Amendment 2 mainly include the following.

- *In the analysis of immunogenicity section, the analysis on GM ratios between anti-RSV F antibody concentrations (IgG Total) and anti-RSV-A neutralising antibody titers at pre-vaccination has been added for Day 90 and final analysis;*
- *In the analysis of immunogenicity section, the analysis on GM ratios of fold increase post/pre (Day 30/Day 0) between anti-RSV F antibody concentrations (IgG Total) and anti-RSV-A neutralising antibody titers has been added for Day 90 and final analysis.*

Changes of TFL/TOC

- *In the analysis of safety section, figures of “Individual results of hemoglobin levels beyond grade 2” will be reported for Day 90 and final analysis to replace the figures of “Individual results of hemoglobin levels outside of normal range”;*
- *In the analysis of safety section, figures of “Individual results of white blood cells counts levels lower than LL” and figures of “Individual results of white blood cells counts levels higher than UL” will be reported for Day 90 and final analysis to replace the figures of “Individual results of white blood cells counts levels outside of normal range”.*
- *In the analysis of immunogenicity section, one new template (Template 54) for “Comparisons of GM ratios with corresponding 95% confidence interval between anti-RSV F antibody concentrations (IgG Total) and anti-RSV-A neutralising antibody titers at pre-vaccination (Per protocol set)” has been added for Day 90 and final analysis;*
- *In the analysis of immunogenicity section, one new template (Template 55) for “Exploratory comparisons (GM ratios of fold increase post/pre) with corresponding 95% confidence interval between anti-RSV F antibody concentrations (IgG Total) and anti-RSV-A neutralising antibody titers at Day 30 (Per protocol set)” has been added for Day 90 and final analysis;*

Changes in Amendment 3 mainly include the following.***Changes of TFL/TOC for final analysis***

- *All tables concerned with ‘Incidence and nature of symptoms (solicited and unsolicited)’ have been moved to Annex; such tables for Grade 3 are kept as in-text tables;*
- *Tables of ‘Incidence of solicited local/general symptoms reported during the 7-day (Days 0-6) post-vaccination period’ have been moved to Annex; such tables by maximum intensity are kept as in-text tables and corresponding figures have been newly generated for the final analysis, that is, ‘Percentage of subjects reporting solicited local/general symptoms (any grade / grade 3) during the 7-day post-vaccination period’;*
- *All tables concerned with ‘Percentage of subjects reporting the occurrence of unsolicited symptoms’ have been moved to Annex; Such tables for Grade 3 and/or considered related to vaccination are kept as in-text tables with the simplification by removing the columns of LL and UL;*

- *Tables of ‘Percentage of subjects reporting the occurrence of SAE within the 30-day (Days 0-29) post-vaccination period/throughout the study period’ are kept as in-text tables with the simplification by removing the columns of LL and UL;*
- *All tables concerned with ‘Number (%) of subjects reporting the occurrence of adverse events’ have been moved to Annex;*
- *All tables of ‘Number and percentage of subjects reporting the occurrence of medically attended respiration tract infections (MA-RTIs)’ have been moved to Annex; MA-RTIs reported up to DBF of final analysis is kept as one in-text table with the simplification by removing the columns of LL and UL;*
- *The table of ‘Compliance in returning symptom information’ and all tables concerned with ‘Number and percentage of subjects taking a concomitant medication’ have been moved to Annex;*
- *The table of ‘Exploratory comparisons between groups in terms of percentage of subjects reported any Grade 2/3 AE and/or any fever >38.5°C and/or any vaccine-related SAE during the 7 day (Days 0-6) Post- vaccination period’ will not be reported in the final analysis;*
- *The table of ‘Distribution of change from baseline in haematology and biochemistry with respect to normal laboratory ranges’ has been moved to Annex; Three splitted in-text tables for ALT/AST /Eosinophils, Creatinine/Lymphocytes/White Blood Cells and Haemoglobin/ platelet count/ Neutrophils have been generated, separately;*
- *The table of ‘Summary of haematology and biochemistry results by maximum grade’ has been moved to Annex; One newly formatted in-text table of ‘Summary of haematology and biochemistry results by maximum grade in the specified category’ has been generated by collapsing the categories of unknown/grade 0 and grade 1 then renaming the new category of ‘other’, keeping grade 2, 3 and 4 column, and removing the column of n;*
- *The table of ‘Summary of haematology change from baseline by maximum grade’ has been moved to Annex; One newly formatted in-text table of ‘Summary of haematology change from baseline by maximum grade in the specified category’ has been generated by collapsing the categories of unknown/grade 0 and grade 1 then renaming the new category of ‘other’, keeping grade 2, 3 and 4 column, and removing the column of n;*

Changes in Amendment 4 mainly include the following.

Please check the dry run meeting minutes for details.

C.A.R.S./Clinical R&D/RSV F/Studies/021 (204812)/11 Statistics/11.05
General/11.05.03 Meeting Material/Analysis E01_01/RSV F-021 (204812) Dry Run
Minutes E01_01.

